7.9 Exclusion criteria

To participate, the women must not meet any of the following exclusion criteria:

- Being pregnant or planning to become pregnant during the study period
- Any previous or current diagnosis of breast cancer (including carcinoma in situ)
- Mammographic BI-RADS code 3 or above at baseline mammography, or at a diagnostic mammography during time of treatment (the first 6 months of the study)
- Any previous diagnosis of cancer with the exception of non-melanoma skin cancer and in situ cancer of the cervix
- Currently using *oral* oestrogen and progesterone based hormone replacement therapy
- Current use of hormone contraceptive with hormones, e.g. hormonal contraceptive pills, or progesterone implants. Hormonal intrauterine devices are accepted.
- A history of thrombo-embolic disease such as embolies, deep vein thrombosis, stroke, TIA or cardiac arrest.
- Known APC (Activated protein C) resistance, an inherited hemostatic disorder
- A history of major surgery of the breast, e.g. reduction or enlargement, which might affect density measurements
- A history of immobilization, e.g. using wheelchair
- Known uncontrolled diabetes
- Hypertension at baseline, defined as systolic pressure higher than 140 mm Hg and diastolic higher than 90 mm Hg
- Use of drugs that interfere with CYP2D6 expression such as Seroxat (paroxetine), Fontex (fluoxetin) and Zyban / Voxra (bupropion)
- Use of Waran (warfarin)
- Non-medical approved drugs against hot-flashes including phytooestrogen
- Not able to understand study information and/or informed consent

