5.2 Risks of side effects

Tamoxifen at a dose of 20 mg has side effects that can be divided into common side effects, that are more or less harmless and reversible, and rarer serious side effects.

The common side effects are menopause symptoms; sweating, hot flashes and insomnia. These side effects disappear shortly after stopping treatment. Women who during the study are bothered by these side effects will obviously be able to cancel participation.

The serious and uncommon side effects include cancer of the uterus. This is extremely rare and perishing of gynecological disorders. A gynecologist is involved in the study and the participants will be encouraged to contact the Karma Study Centre if they experience problems.

Another serious and uncommon side effect is blood clots. It's the same kind of problems that can arise when using oral contraceptives. It should be emphasized that the rare side effects only have been observed for tamoxifen use in doses of 20-40 mg for at least 2 years. The spectra of side effects at lower doses and shorter treatment times are unknown.

By applying strict exclusions criterias, such as a history of trombo- embolic disease, hypertension or use of hormonal contraceptive pills we will minimize the risks we expose to the participants.

Participants will report side effects after 1, 3, and 6 months (and the Lund cohort will also report after 12 months). They will also report side effects whenever they occur and there is also an alarm system when adverse events, that need to be followed up, are reported in the web questionnaire form or in the application called Karmapp installed in their smartphone or tablets. Participants will be informed to contact the Karma Study Centre immediately if they suspect side effects. The contact channels are Karmapp, phone or email and they will be manned during long-weekends and holidays seasons on a jour basis.

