7.1.2 Pre-screening of eligibility of participation

At Karma Study Centre:

- 1) A Karma staff checks that the woman has read and understood the study information.
- 2) Volpara density measurement data are retrieved from the performed mammographic examination in order to see that the women meet inclusion criteria for density (≥4.5 % volumetric density)

3) Blood pressure is measured to ensure eligibility to participation.

If it at this stage turns out that the woman doesn't meet inclusion criteria or meet any of the exclusion criteria, she will have an explanation from investigator why she can't participate. A recording of non-participation is done in the Study file screening-list.

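### The hypertension exclusion in Protocol 7.9 joins its two limits with 'and', so as written one raised value does not exclude a woman, although Protocol 5.2 relies on excluding hypertension to limit risk

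*Protocol*

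**What the plan says.** Protocol section 7.9 opens its list with the rule "To participate, the women must not meet any of the following exclusion criteria". One entry in that list reads "Hypertension at baseline, defined as systolic pressure higher than 140 mm Hg and diastolic higher than 90 mm Hg". It is the only entry that concerns blood pressure. None of the others covers a known or treated diagnosis of hypertension.

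Protocol section 5.2 sets out how the risk of side effects is contained. After discussing blood clots, it gives examples of strict exclusion criteria, starting with thrombo-embolic history and continuing "hypertension or use of hormonal contraceptive pills we will minimize the risks we expose to the participants". Hypertension appears there with no definition and no qualification.

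Protocol section 7.1.2 gives the operational step: "Blood pressure is measured to ensure eligibility to participation". It states no limit of its own. The schedule of events in Appendix 14.3 marks blood pressure in the baseline column only. The 6- and 12-month visits in sections 7.1.6 and 7.1.7 list weight, length and waist, but not blood pressure. The SAP's population section (4.1) contains no blood pressure criterion.

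**The concern.** The risk-benefit argument and the operative entry rule do not clearly describe the same population. A reader of 5.2 would take it that women with hypertension are kept out. A staff member who applies 7.9 as worded keeps out only women above both limits at once.

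What is at stake is participant safety. By the protocol's own account in 5.1, taking part brings no obvious individual advantage. Five of the six arms receive tamoxifen, and 5.2 says that the side-effect profile at lower doses and shorter treatment is unknown. In that setting an entry safeguard should mean what the risk section says it means. Since blood pressure is planned only at entry, the wording of this one criterion decides how the only scheduled reading is used.

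A second, smaller issue is consistency. If the intended meaning was different from the literal one, different staff could classify the same reading differently.

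**Working it through.** No sample size, power or alpha figure bears on this point, so there is no plan figure to reproduce. The check is logical.

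**Inputs**
- Systolic limit: higher than 140 mm Hg (Protocol 7.9).
- Diastolic limit: higher than 90 mm Hg (Protocol 7.9).
- Connective: 'and' (Protocol 7.9).
- Meeting any one listed criterion excludes; a woman who does not meet the definition is not excluded by that entry (Protocol 7.9).

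**Step 1. The two readings of the rule**
- Literal: exclude if SBP > 140 and DBP > 90.
- Alternative: exclude if SBP > 140 or DBP > 90.

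**Step 2. Apply both to readings chosen to lie on either side of the limits**

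| Reading | Literal rule | Alternative rule |
|---|---|---|
| 130/80 | not excluded | not excluded |
| 140/90 | not excluded | not excluded |
| 141/90 | not excluded | excluded |
| 170/80 | not excluded | excluded |
| 140/91 | not excluded | excluded |
| 130/105 | not excluded | excluded |
| 141/91 | excluded | excluded |
| 170/105 | excluded | excluded |

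The two readings differ exactly for women with one value above its limit and the other not above it. The literal rule sets no ceiling on the single raised value. These are illustrations, not a sample of participants.

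**Step 3. Look for another provision that closes the gap**
- 7.1.2 measures blood pressure for eligibility but gives no threshold, so it points back to 7.9.
- Appendix 14.3 schedules the reading at baseline and gives no threshold.
- The other vascular entries in 7.9 (thrombo-embolic history, known APC resistance, immobilisation, uncontrolled diabetes, warfarin, hormonal contraceptives and oral HRT) do not depend on blood pressure.
- 7.10 lets the investigator take a woman out where medically necessary, but that section governs withdrawal, not entry.

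**Step 4. Set 5.2 beside 7.9**

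Section 5.2 relies on excluding hypertension and calls the criteria strict. Section 7.9 supplies the only definition, and its literal form is the more permissive of the two readings. Nothing in 5.2 tells the reader that women with one raised value may be enrolled.

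**Step 5. Size**

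The documents give no blood pressure distribution for women aged 40-74 in the screening programme. The number of women with exactly one raised value therefore cannot be calculated, and the point does not depend on it.

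**The case against.** The strongest reply is that there is no head-on contradiction. Section 5.2 uses hypertension as a summary term in a list of examples, and 7.9 defines it; a term defined elsewhere is not a clash. The 'and' may also be no more than a loose way of listing two limits. The same list uses 'and' loosely when it names the two cancers that are permitted, although it uses 'or' and 'and/or' for alternatives elsewhere. The eCRF check and any site instructions are not among the documents, so what staff actually apply is unknown. Blood pressure is one of several vascular-risk criteria, an investigator meets each woman before randomisation, and 5.2 notes that the rare serious effects have been seen only at 20-40 mg for at least 2 years, against 6 months of treatment here.

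Much of this stands as a limit on what can be claimed. It does not remove the need to correct the text. If 'and' is meant literally, 5.2 promises more than 7.9 delivers; if it is meant loosely, the operative criterion does not say what is intended.

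A reader might be tempted to go further in four ways, none of which the documents support:
- That a woman with one raised value is necessarily randomised. She is only not excluded by this criterion; the other criteria still apply.
- That 5.2 proves that either value alone was meant to exclude. It contains no threshold and cannot settle that.
- That the two sites would enrol materially different populations. Section 5.4 plans about 40 women in Lund out of 1,440, and 40/1,440 = 2.8%. Inconsistency between staff is the more relevant risk.
- That a count of affected women can be given. Any prevalence would be a guess.

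**Conclusion.** The point holds as a safety-wording defect in an operative eligibility rule. As written, 7.9 does not exclude a woman with only one value above its limit. Section 5.2 relies without qualification on excluding hypertension, and no other provision covers a single raised value at entry. With no later reading scheduled, the entry check is the only planned occasion on which it would be noticed.

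The conclusion rests on the literal reading of 'and'. If the authors meant it loosely, the defect becomes an ambiguity in the same criterion, and the correction needed is the same.

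The size in women cannot be stated. The endpoint, margin, sample size and power do not depend on this criterion. Eligibility is settled before randomisation and the arms are evenly distributed within blocks, so there is no reason to expect bias between arms. The case for acting is participant protection and a criterion that is applied to every candidate.

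**What to change.** Reconcile 7.9 with 5.2:
- In 7.9, state explicitly whether one or both values must exceed the limit for a woman to be excluded.
- In 5.2, describe the protection that this rule actually delivers, including whether women with a single raised value may be enrolled.
- Carry the same wording into the pre-screening step in 7.1.2 and the eCRF eligibility check.

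Which rule and which limits apply is a clinical decision for the sponsor, and no view on it is given here.

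The cost is a short amendment and an aligned eCRF check. No new procedure is needed, because blood pressure is already measured at entry. Depending on the rule chosen, there may be some more screen failures.

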7.10 Criteria for withdrawal

The Subject should be excluded from the study if, in the opinion of the Investigator, it is medically necessary, or if it is the expressed wish of the subject. Women are free to discontinue their participation in the study at any time.

Irrespective of the reason for withdrawal and whenever possible, the subject should be encouraged to return for a clinical visit at the time of or soon after discontinuation and complete

all evaluations which may be necessary to assure that the subject is free from any untoward effects and to perform appropriate follow-up for any continuing medical event. Relevant laboratory test samples should be obtained and all relevant assessments should be completed, preferably according to the scheme for the final assessment. The eCRF should be completed as far as possible.

A withdrawn subject is not allowed to re-enter into the study. The criteria for withdrawal are the following:

- A woman develops breast cancer, including ductal carcinoma in situ (DCIS).
- Subject wishes to discontinue
- Unacceptable adverse event/side effect
- Non-compliance with the study protocol
- Subject refuses to cooperate
- Other medical reasons
- Pregnancy

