5.5 Risk-benefit of frequent mammograms

Eligible study participants will only be women that have negative screening mammograms before entering the study, i.e. no abnormalities have been identified. The participants will have extra mammograms taken at 6 (all participants) and 12 (only Lund cohort) months after study entry. In order to reduce radiation exposure, the mammograms consist of 2 images instead of 4, which are standard at a screening examination. The images will be used for density measurement but radiologist will also screen them for abnormalities as in clinical practise. It could be that some few cancers are diagnosed at these extra visits, which should be seen as something that benefits the study participants.

If a suspected alteration is seen, women will receive the normal routine work-up for a suspected breast cancer, that is, additional ultrasound examination and a possible fine needle biopsy. Surgical interventions are only performed if a cancer is detected.

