- 7.1.6 6 months after baseline (+/- 2 weeks), End of treatment all participants, end of study SöS-cohort

Visit at Karma Study Centre:

- Karisma II follow up questionnaire including general symptoms, tamoxifen related symptoms, compliance and health care contact connected to possible side effects
- In total 24 ml blood will be collected. Planned analyses are tamoxifen metabolites, plasma hormones, plasma proteins, metabolic markers.
- Mammogram (one image per breast only for density measurement purposes)
- Measurement of weight, length and waist
- A 2nd biopsy will be performed if participation at baseline

End of study SöS cohort. The women will be informed that the study period now has ended and she will be called to mammography within the national screening program.

7.1.7 12 months after baseline (+/- 2 weeks), End of study Lund cohort

Visit at Karma Study Centre:

- Karisma II follow up questionnaire including general symptoms, tamoxifen related symptoms, compliance and health care contact connected to possible side effects
- Mammogram (one image per breast only for density measurement purposes)
- Measurement of weight, length and waist
- Meeting with Investigator (Group meeting)

The women will be informed that the study period now has ended and she will be called to mammography within the national screening program.

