7.1.9 Reminders

Women will receive e-mail/sms reminders regarding their upcoming appointment and/or web-questionnaire to complete.

Women not showing up at regular visits at the Karma Study Centre or fail to submit follow-up questionnaires will be contacted to ensure compliance and to ensure that no adverse events have occurred.

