7.2 Dropouts

Participation in the Karisma II study is voluntary and the study participant may end her participation at any time. There may however be a scientific value to continue investigating the effects of tamoxifen after the participant discontinues her treatment to tamoxifen. Women that drop out after 1 week or more, will therefore be asked to still attend the planed follow-up questionnaires, blood sampling, exit-mammogram and biopsy if applicable. This is however not a mandatory request and the study participant is free to decline. The time limit of exit exams is set to 2 weeks after stop of medication.

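### Protocol 7.10 makes non-compliance a reason to leave the study, and 7.2 offers early leavers no month-6 mammogram, although the primary analysis is ITT on change to month 6 (cheap improvement)

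*Protocol*

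**What the plan says.** **Withdrawal.** Protocol 7.10 opens by limiting exclusion from the study to cases "if, in the opinion of the Investigator, it is medically necessary, or if it is the expressed wish of the subject". Its list of criteria then includes "Non-compliance with the study protocol" as a separate item, next to the woman's own wish, adverse events, refusal to cooperate, pregnancy and breast cancer. It gives no threshold, and it adds: "A withdrawn subject is not allowed to re-enter into the study". A closing visit at or soon after discontinuation is encouraged.

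**Follow-up after leaving.** Protocol 7.2 asks women who drop out after a week or more to complete the planned questionnaires, blood sampling and an exit mammogram. Of this it says: "This is however not a mandatory request and the study participant is free to decline". On timing it says: "The time limit of exit exams is set to 2 weeks after stop of medication".

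**Scheduled density.** Protocol 7.1.6 sets the visit at "6 months after baseline (+/- 2 weeks), End of treatment all participants". Protocol 5.5 says: "The participants will have extra mammograms taken at 6 (all participants) and 12 (only Lund cohort) months after study entry". Up to month 6 this is the only scheduled post-baseline mammogram.

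**Analysis.** The primary analysis is ITT on the decrease from baseline to 6 months (Protocol 10.6.2; SAP 6.3), with last observation carried forward (SAP 6.9). SAP 6.1 admits a woman to the ITT set only if she has at least one post-baseline measure. The 80% tablet rule (Protocol 7.11.8 and 10.6.2) serves in SAP 6.1 to define the per-protocol set. Compliance on the Morisky scale is also a tertiary endpoint (SAP 5.5 and 5.6).

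**The concern.** An ITT comparison at month 6 needs month-6 density whatever the drug use. SAP 6.9 defends the primary analysis on effectiveness grounds, which is the same requirement. A criterion that takes women out of the study because they did not comply removes some of the women that ITT is meant to keep. The criterion also conflicts with the opening sentence of its own section: non-compliance is neither a medical necessity nor the woman's wish. With no threshold, two investigators could apply it differently.

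Once a woman has left, 7.2 decides what is measured and when. The exit exam is tied to the date she stops drug, not to month 6. Some primary outcomes would therefore be measured early and treated as month 6, or not measured at all, although a visit that could capture them is already scheduled.

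**Working it through.** **1. What each section does with a woman who does not comply.**

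| Place | Consequence |
|---|---|
| Protocol 7.10, opening sentence | None; exclusion is for medical need or her own wish |
| Protocol 7.10, list | Leaves the study, no re-entry, no threshold |
| Protocol 7.1.9 | Contacted if she misses a visit or questionnaire |
| Protocol 7.11.8 | Classed as a complier or not, by tablet count at the final visit and by web questionnaire |
| SAP 6.1 | Out of the per-protocol set; ITT status unaffected |

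Only the list in 7.10 ends her participation. If non-compliance is found by tablet count at the final visit, no density is lost, because the mammogram is due at that visit. The 7.10 line can affect density only if it is applied before month 6, for example after the month-1 or month-3 questionnaire, both of which ask about compliance.

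**2. Can the exit mammogram serve as the month-6 value?** The inputs are a month-6 visit of ±2 weeks (7.1.6), an exit exam at most 2 weeks after stopping drug (7.2), and 4.348 weeks per month.

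- Month 6: 6 × 4.348 = 26.1 weeks.
- Window opens: 26.1 − 2 = week 24.1.
- Drug stop before which the exit exam cannot reach the window: 24.1 − 2 = week 22.1, or month 5.1 (22.1 / 4.348).
- Share of the treatment calendar: 22.1 / 26.1 = 85%.
- Drug stopped at month 1: exit exam by 4.35 + 2 = week 6.3, which is 17.7 weeks before the window opens (unrounded inputs).
- Drug stopped at month 3: exit exam by 13.04 + 2 = week 15.0, which is 9.0 weeks before the window opens.
- Drug stopped after week 22.1: the exit exam can fall in the window, and nothing need be lost.

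This timing applies to every early leaver, whatever the reason.

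**3. What the SAP then does.** If she has the exit mammogram, that value is carried forward as month 6. If she declines it and has no other post-baseline value, she is not in the SAP's ITT set. Month-6 density is imputed for women who dropped out only in sensitivity analyses (SAP 6.9).

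**4. Link to the planned sample size.** The documents' formula with one-sided alpha 0.015, 80% power, 50% responders in both arms and a 16.7-point margin gives (2.170 + 0.842)² × (2,500 + 2,500) / 16.7² = 162.6, so 163 per arm against the stated 168. The drop-out step is exact: 168 / (1 − 0.30) = 240. The plan thus already allows for 30% of women contributing nothing. It gives no breakdown by reason, so the share due to non-compliance cannot be derived.

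**The case against.** The strongest objection is that 7.10 is the wrong target. The mistimed density comes from the exit-exam rule in 7.2, which covers every drop-out after a week; deleting the non-compliance line would leave that rule in place. This stands. A reader might infer that 7.10 alone causes the loss, and the documents do not support that. What 7.10 adds is a route by which a woman who has not asked to leave can enter that group.

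Second, the group withdrawn for non-compliance before month 6 may be nearly empty. All drug is dispensed at baseline, there is no site visit until month 6, and the tablet count is at the final visit. Women who miss a visit or questionnaire "will be contacted to ensure compliance and to ensure that no adverse events have occurred", not to be removed. SAP 6.1 presupposes that non-compliers can stay and be measured, and SAP 5.6 makes compliance an endpoint. This stands as a limit on size. It also shows that the line in 7.10 does not fit the rest of the plan.

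Third, an exam close to stopping captures density near drug exposure, and density after cessation is a separate tertiary question. That is a fair reason to keep the exit exam as a fallback. It does not make an early value a month-6 value, which the primary endpoint requires.

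Fourth, inviting only non-compliers to month 6 would make outcome timing differ by reason for stopping. In the pilot about 25% of women stopped for adverse events, so they are likely to be a large group. This stands, and the invitation should therefore go to all early stoppers.

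Finally, the drop-out allowance, the per-protocol analysis, multiple imputation and tipping-point analyses all mitigate. The last two are sensitivity analyses, and imputation models a value that an existing visit could observe.

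**Conclusion.** The point holds in a limited form. A stated rule that removes non-compliers conflicts with the plan's effectiveness-based ITT aim. For any woman who stops drug before about week 22, the only mammogram offered cannot be a month-6 value. The timing rests on the ±2-week window and the 2-week exit limit, both taken from the protocol.

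Three stronger readings are tempting, and the documents support none of them.

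- **Loss of power.** Under the plan's assumptions, nominal power is about 81% at 168 per arm and 93% at 240. A reader might take the difference as the cost of this rule. It would require month-6 density from every planned drop-out, for any reason, and women with an exit mammogram already count in the ITT set.
- **Direction of bias.** The SAP expects ITT with carried-forward values to lean towards equivalence if non-compliance depends on dose. That condition is untested, and the pilot saw no dose-dependent difference in discontinuation between 10 and 20 mg.
- **85% of women.** The figure is a share of the treatment calendar, not of participants.

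The effect is probably small and cannot be quantified from the documents. This is a cheap improvement of low severity.

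**What to change.** - **Protocol 7.10:** make non-compliance at most a reason to stop study drug, not to leave the study. The woman remains free to leave, and the other criteria are unchanged.
- **Protocol 7.2:** invite every woman who stops drug early and has not withdrawn consent, except for pregnancy or breast cancer, to the scheduled month-6 mammogram. Timing then does not differ by reason for stopping. Keep the exit exam within 2 weeks as the fallback for those who will not return.
- **Analysis:** keep these women in ITT and exclude them from per-protocol. A short clause in SAP 6.1 would help, because remaining in the study for 6 months would no longer imply remaining on drug. Leave the drop-out endpoint in SAP 6.4 unchanged.

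The cost is about one line in each protocol section and an amendment, with ethics and authority approval if the change is judged substantial (Protocol 10.5). No new visit type is needed. The downside is that some density will be measured off drug; the per-protocol and imputation analyses already planned can set that in context.
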